5.1.2 Liver transplantation

Patients randomized to liver transplantation will be listed on the extended donor criteria (EDC) waiting-list when the MDT meeting consider the patients a candidate for liver transplantation. The

oncologist and transplant surgeon will decide if the patient should continue on chemotherapy after being listed for transplantation. Patients treated with bevacizumab will stop bevacizumab at time of being listed for transplantation.

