3 OVERALL STUDY DESIGN/OVERVIEW OF DESIGN

EXCALIBUR is a phase II study.

Excalibur 1 is a three-armed RCT comparing 2nd line systemic chemotherapy to liver transplant and to HAI. Because of the transplant arm, this sub-trial has somewhat stricter inclusion criteria.

Excalibur 2 is a two-armed RCT conducted within the same framework as *Excalibur 1*, but without the transplant arm, and with somewhat wider inclusion criteria (see figure). For analysis, the HAI arm and the systemic chemotherapy arm of *Excalibur 1* and 2 will be directly comparable (stratified for age and primary tumour resected/in situ) and hence boost numbers for this comparison.

[figure not shown]
Study period:

Estimated date of first patient enrolled: February 2021

Anticipated recruitment period: 3 years

Estimated date of last patient completed: November 2024

Treatment duration: up to 2 years

- HAI (intervention group 2) and Systemic therapy (control arm, group 3): Until progression or resection, up to two years
- Transplant (intervention group 1): Until transplant or until removal from list.

Follow-up for outcomes: 10 years

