 - Monthly pregnancy testing should be performed in women of childbearing potential (WOCBP) as long as they receive chemotherapy according to study protocol. This can be done with a urine test at home combined with contact with the study team by phone
 - A calendar for oncologist visits and provision of systemic chemotherapy is created by coordinating nurse. Control scans are ordered for each 2nd month for the first year following randomization and as long as the patients receive chemotherapy, each 3rd month for the second year and each 6th month for the third year. MDT meetings are scheduled for one week following each new scanning to assess response and possible resectability
 - Out-patient control appointments are scheduled for outcome assessment including QoL-scoring (3, 6, 9, 15, 18, 21 and 24 months)
- Patients in HAI group (group 2 a and 2b)
 - A calendar of reservoir refills is created and harmonized with provision of systemic treatment.
 - A laparotomy is performed within 2 weeks from randomization with insertion of catheter and reservoir for HAI-pump.
- Patients in transplant group
 - Oncologists are instructed to avoid Avastin in systemic chemotherapy while the patient is listed.

Table 3: Overview of screening procedures, End of study/Withdrawal

Overview of screening procedures, End of study Withdrawal												
Item	ICF	Inc/Ex	Med Hist	Prior Trea	Phys Exam	Vit Sign	ECOG	CT/ MR	QoL	Blood Sample	Adverse Event	Survival Assessment
Screening	x	x	x	x	x	x	x	x	x	x	x	
EOS/Withdrawal											x	x

Table 4: Calendar of cycles and events for patients in HAI group

Calendar of cycles and events for patients in HAI group								
Day cycle 1 + 2	1	2	15	16	29	30	44	
Day cycle 3 + 4	61	62	75	76	89	90	104	
Pump refill FUDR at OUS	x				x			
Pump refill HepNaCl at OUS			x					x
Systemic chemo local hospital		x		x		x		

Table 5: Calendar of cycles and events for patients in control group and on waiting list for LTx-group

Calendar of cycles and events for patients in control group and on waiting list for LTx- group							
Day cycle 1 + 2	1		15		29		44
Day cycle 3 + 4	61		75		89		104
Systemic chemo local hospital	x		x		x		x

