5.6.1 Before Treatment Starts

Eligible and consenting patients will be randomized. Patients randomized to systemic chemotherapy will receive chemotherapy at their local hospital. Patients randomized to HIA and systemic chemotherapy will have the pump placement and HAI administration at the department of gastrointestinal surgery/HPB section at OUH/Rikshospitalet. The systemic chemotherapy will be administered at local hospitals. The patients in these two groups will repeatedly be evaluated for liver resection at the MDT-meeting at Rikshospitalet and patients who become resectable will have liver resection/local ablation at Rikshospitalet. Patients randomized to liver transplantation will be evaluated for liver transplantation and receive liver transplantation according to standard procedure at the department of Transplantation Medicine, Rikshospitalet. These patients will receive chemotherapy at their local hospital until time of receiving a liver transplant.

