5.6.3 Progressive disease or toxicity

In the case of progressive disease (PD) in the systemic chemotherapy arm, this treatment will be halted and shifted to 3rd chemotherapy as appropriate or to best supportive care (BSC). In the case of PD in the HAI-group, systemic chemotherapy will be changed to 3rd line as appropriate and the use of pump is discontinued. In the case of PD in the transplant group, listing is upheld but chemotherapy is changed to 3rd line as appropriate until available organ is available. In the case of toxicity a change in systemic chemotherapy to 3rd line is attempted and if unaltered toxicity, halted.

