5.6.5 After End of Treatment (Follow-up)

Patients having a liver resection or liver transplantation will have follow-up according to Table 6-7. These patients will have follow-up until 10 years after surgery or until they start palliative treatment.

Table 6. Follow-up of resected Excalibur study patients

Follow up Ltx patients	Visits 1 st year (every month)	Visits 2 nd year (every 3 month)	Visits 3 rd -10 th years (every 6 month)
Hb CRP, Hv, Trc, Na, K, Crea	X	X	X
Bilirubin, ASAT, ALAT, ALP, Alb	X	X	X
INR, Cholesterol, glucose, HbA1c	X	X	X
CEA, CA 19-9,	Every 3 months	X	X
TIMP-1, TPA (stop at relapse)	Every 3 months	X	X
5 ml EDTA plasma for later analyses (until relapse)	Every 3 months	X	X
5 ml serum for later analyses (until relapse)	Every 3 months	X	X
Weight	X	X	X

BP	X	X	X
CT thorax/abdomen/pelvis (only in Ltx patients without relapse)	Every 2 months	Every 3 months	Every 6 months
US Liver w/Doppler (only Ltx patients)	Every 3 months		
Coloscopy (only in Ltx patients without relapse)	At 12 months	At 36 months	At 60 months
PET scan (only in patients without lesions on CT)	At 12 months	At 24 months	
EORTC QLQ-C30 and EQ5D	3, 6, 12, months	2 times/year	2 times 3.year

Table 7 Follow-up of Control group, HAI-group and patients not receiving LTx

arm		Outcome	Palliative treatment	Follow Up
3 and 2	Chemo therapy	Surgery	No	10 Years
	FUDR/HAI	PD/Toxicity	yes	Will do "End of treatment visit". OS will be collected.
1	Liver Tx	Transplant	No	10 Years.
		Extra-hepatic disease	yes	Will do "End of treatment visit". OS will be collected.
		Metastasis to lymphnodes	yes	Will do "End of treatment visit". OS will be collected.

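### For a transplant-arm patient with extra-hepatic or nodal progression, Section 5.6.3 keeps the listing and Table 7 ends the pathway; chemotherapy after listing is also stated inconsistently

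*Protocol*

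**What the plan says.** **Staying listed after progression**

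- Protocol Section 5.6.3: "In the case of PD in the transplant group, listing is upheld but chemotherapy is changed to 3rd line as appropriate". The site of progression is not distinguished.
- Protocol Section 5.6.5, Table 7, arm 1: the outcomes "Extra-hepatic disease" and "Metastasis to lymphnodes" are each marked for palliative treatment and an end-of-treatment visit, with survival collected afterwards.
- Protocol Section 3 gives the treatment duration of the transplant arm as "Until transplant or until removal from list". No section says what triggers removal.

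**Chemotherapy between listing and transplantation**

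- Section 5.1.2: the "oncologist and transplant surgeon will decide if the patient should continue on chemotherapy after being listed for transplantation".
- Section 5.6.1: "These patients will receive chemotherapy at their local hospital until time of receiving a liver transplant".
- Section 5.5, Table 5, has the title "Calendar of cycles and events for patients in control group and on waiting list for LTx-group" and gives both groups the same treatment days.
- Section 5.6.3 changes chemotherapy to third line on progression while the patient waits for an organ.
- Section 5.6.4 ends systemic chemotherapy at progression and does not except the transplant arm.

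The bevacizumab instructions in Sections 5.1.2 and 5.5 agree with each other and are not part of this point.

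**The concern.** The transplant arm is in the trial as a proof of principle, to benchmark what the sponsor expects to be the best treatment (Section 1.7). Its estimate is informative only if the reader knows which patients were carried through to transplantation and which were taken off the pathway. For one foreseeable course, spread outside the liver while waiting, the protocol gives two incompatible instructions, and the choice decides whether the patient can still receive an organ. The trial is open label, so that choice is made with the arm known.

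Three planned results depend on it directly: the transplantation rate (Section 8.5.2), the per-protocol set, and the set of patients who actually received the allocated transplant (both Section 8.3).

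The chemotherapy wording also matters for conduct. Stopping chemotherapy after listing is allowed by Section 5.1.2 but departs from Section 5.6.1. Section 5.7 makes a major protocol deviation a ground for discontinuing a patient, and Section 9.2 requires significant deviations to be reported.

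**Working it through.** The contradiction is textual, so the main check is to set the sections side by side. Arithmetic serves only to size the arm.

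**Step 1. Is extra-hepatic or nodal spread progression in this arm?** The additional exclusions for Excalibur 1 (Section 4.3) bar any sign of extra-hepatic metastatic disease or local recurrence, except up to three resectable lung lesions of at most 15 mm. Extra-hepatic or nodal disease that appears later in a transplant-arm patient is therefore, in general, new since entry. It falls under the progression rule of Section 5.6.3, which carries no exception.

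**Step 2. Apply each rule to the same patient.**

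| Course while listed | Section 5.6.3 | Table 7, arm 1 | Compatible? |
|---|---|---|---|
| Progression in the liver only | Stays listed, third-line chemotherapy | No row | Yes |
| New extra-hepatic disease | Stays listed, third-line chemotherapy | Palliative treatment, end-of-treatment visit | No |
| New lymph-node metastasis | Stays listed, third-line chemotherapy | Palliative treatment, end-of-treatment visit | No |

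Section 3 could settle the last two rows if it defined removal from the list, but it does not.

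**Step 3. Chemotherapy after listing.** Section 5.1.2 makes continuation a decision for each patient. Section 5.6.1 states it as what happens, and Table 5 schedules it. On progression, Section 5.6.3 switches it and Section 5.6.4 stops it.

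**Step 4. The plan's figure for the arm.** Inputs from Section 8.1: 2-year survival 30% in controls and 90% with transplantation, two-sided alpha 0.05, power 0.80, 16 controls and 7 transplant patients, so k = 7/16. With pooled variance under the null:

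n(control) = [1.960 × √((1 + 1/k) p̄(1 − p̄)) + 0.842 × √(p₁(1 − p₁) + p₂(1 − p₂)/k)]² / (p₂ − p₁)²

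p̄ = (0.30 + 0.4375 × 0.90)/1.4375 = 0.483. This gives 15 controls and 15 × 7/16 = 6.6, so 7 transplant patients. Power at 16 against 7 is 0.83. With 15% drop-out, 7/0.85 = 8.2, so 9. The plan's 7 completed and 9 randomised transplant patients reproduce.

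**Step 5. Weight of one patient.** 1/9 = 11.1 percentage points. Handling one patient under the other rule can move the transplantation rate by that amount. It moves 2-year survival only if it changes whether that patient is alive at two years.

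**Step 6. Illustration, on an assumption that is not in the documents.** Suppose each transplanted patient has 90% and each untransplanted patient 30% 2-year survival. With m of 9 untransplanted, arm survival is [(9 − m) × 0.90 + m × 0.30]/9. Power is for the Section 8.1 test of proportions at 18 against 9.

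| m | Arm survival | Power |
|---|---|---|
| 0 | 90% | 0.91 |
| 1 | 83% | 0.79 |
| 2 | 77% | 0.65 |
| 3 | 70% | 0.51 |

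The assumption probably overstates the effect, because it gives a patient with extra-hepatic progression the full 90% if transplanted. If transplantation made no difference to such a patient, the handling would not change arm survival at all. The range therefore runs from no change to the table's values.

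**The case against.** **Table 7 is a follow-up table, not a delisting rule.** It stands under follow-up after end of treatment, and its title covers patients who do not receive a transplant. It can be read as recording what is collected once a patient has already left the pathway. On that reading the two texts fit together: progression in general keeps the listing, and extra-hepatic or nodal disease ends it. But Section 5.6.3 states no such exception and Section 3 supplies no criterion, so this reading has to be added by the reader. The objection does narrow the point to those forms of progression.

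**Chemotherapy after listing is a stated discretion.** Section 5.1.2 is the specific clause, Section 5.6.1 mainly says where treatment is given, and Table 5 can be read as the calendar for chemotherapy when it is given. Section 5 leaves second-line chemotherapy to the oncologist in every arm. Section 5.6.4 may refer only to the current regimen. Much of this stands. The chemotherapy part is an inconsistency of wording and is the lesser of the two.

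**Stronger readings that the protocol does not support.**

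- A reader might infer that the arm has no single defined strategy. Section 5 names it: second-line chemotherapy and liver transplantation. The uncertainty concerns conduct after listing and after progression.
- A reader might infer that one death would defeat the arm, since 8/9 = 88.9% is below 90%. The 90% is a planning assumption. The primary analysis is a Cox hazard ratio against standard care (Section 8.5.1).
- A reader might infer that the randomised comparison is invalid. It is not: every randomised patient is analysed as allocated, and survival is collected under either rule.

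**Conclusion.** The contradiction on listing holds for extra-hepatic and nodal progression and needs correction, because the protocol cannot be followed both ways and the choice decides whether a patient remains a candidate for an organ. It does not extend to progression confined to the liver. The chemotherapy inconsistency is real but milder and should be tidied in the same amendment.

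No figure in the sample size section changes, and the intention-to-treat comparison stands. The effect falls on who is transplanted, and so on the transplantation rate, the per-protocol and actually-transplanted sets, and what the benchmark estimate describes. One patient carries 11 percentage points of the rate in the planned arm of nine. Any effect on survival or power depends on the assumption in Step 6 and on how many patients progress in this way while listed, which the protocol does not say. The point also rests on treating new spread outside the liver as progression, which follows from the Excalibur 1 entry criteria. No view is taken on which clinical rule is right.

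**What to change.** 1. Reconcile Section 5.6.3, Table 7 and Section 3 into one statement of which forms of progression keep the listing and which end it. Refer to that statement wherever Section 3 speaks of removal from the list.
2. Reconcile Sections 5.1.2, 5.5 (Table 5), 5.6.1, 5.6.3 and 5.6.4 into one statement on chemotherapy between listing and transplantation, including what happens to it on progression.

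The sponsor's clinicians choose both rules.

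The cost is amendment wording, with no extra patients, visits or procedures. Section 7.2 already requires the records to show treatments given, their changes and timing, and the date of and reason for discontinuing study treatment. It is enough to confirm that removal from the list, with its date and reason, is captured there.

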5.1.3 Hepatic Artery infusion (HAI)

Hepatic artery infusion will be administered via a pump (Tricumed IP2000V (tricumed Medizintechnik GmbH, [name]) titan infusion pump with a 35 ml reservoir (product no. 200 V 025 035 0WA) connected to a Brown silicone intraarterial catheter. The catheter is inserted into the gastroduodenal artery during a formal laparotomy. The treatment will be administered as established as standard operating procedure at Memorial Sloan Kettering Cancer Centre as previously described¹⁴⁻¹⁶. Patients in the HAI group will also receive systemic chemotherapy.

5.1.4 Surgical procedure

5.1.4.1 Placement of the pump.

The pump (Tricumed IP2000V Infusion Pump, 35ml, CE number: I7120728744042) for HAIP chemotherapy is compatible with the use of intravascular infusion of floxuridine. The Pump Catheter 1000 of Tricumed (CE number: I7120728744042) will be connected to the intra-arterial catheter of B.Braun, (CE: 04430042), which has beads that allow for securing the catheter with non-absorbable ties in the gastroduodenal artery (GDA). The two catheters are linked with the Catheter Connector 2000 of Tricumed (CE number: I7120728744042).

Figure A. The Tricumed IP2000V pump

5.1.4.2 HAIP catheter placement

The catheter is positioned in the GDA allowing perfusion of the entire liver without obstructing the flow in the hepatic artery. In patients with abnormal hepatic arterial anatomy, the GDA is still the preferred site, as long as it connects with a proper hepatic artery perfusing of the liver.

Perfusion of the entire liver can be achieved in these patients by ligating all accessories and replaced hepatic arteries. Intrahepatic shunts will typically reassure that the catheter perfuses all liver segments, which can be confirmed intraoperatively with a bolus injection of methylene blue in the pump after clamping accessory and replaced hepatic arteries.

If the GDA is not suitable for catheter placement because of small calibre (rare) or absence of the GDA, the bifurcation of the proper hepatic artery into a left and right hepatic artery can be used. After an (extended) hemihepatectomy, the stump of the artery of the resected liver can be used as a conduit for the catheter. In minor liver resections, the left hepatic artery can be sacrificed for retrograde placement of the catheter with perfusion of the right hepatic artery, resulting in cross-perfusion of the entire liver through intrahepatic shunts. Cross-perfusion can sometimes not be confirmed intraoperatively. However, most patients will eventually develop cross-perfusion after four weeks, as will be ascertained with a postoperative nuclear scan.

5.1.4.3 Technique HAIP catheter and pump placement

The common hepatic artery (CHA) and the GDA are both palpable superior to the body of the pancreas and the first portion of the duodenum. The GDA runs parallel to and lies immediately to the left of the common bile duct, and it is advisable to start by dissecting the CHA to minimize the risk of injuring the bile duct. The right gastric artery is ligated and divided. The distal CHA, the entire GDA, and the proximal proper hepatic artery are dissected circumferentially from their attachments. The full length of the extra-pancreatic GDA is mobilized over 2-3 cm to facilitate insertion of the catheter. Suprapyloric side-branches of the GDA are often encountered and must be ligated. Frequently, branches to the pancreas and duodenum arise from many of these dissected vessels, and it is essential to identify and ligate these branches to avoid inadvertent perfusion of the pancreas, stomach, or duodenum. The common hepatic artery is mobilized 1 cm proximally, and the proper hepatic artery is mobilized about 2 cm distally from the origin of the GDA. Branches to the retroperitoneum from the right or left hepatic artery are common and should be ligated. Review of preoperative CT angiography to look specifically for these branches is important, because they are often found in retrospect. At this point, a complete circumferential dissection of the common hepatic artery, GDA, and proper hepatic artery should be ensured such that no vessels to the pancreas, stomach, or duodenum remain. The GDA should be temporarily occluded with palpation of the proper hepatic artery to rule out retrograde flow to the liver through the GDA secondary to celiac artery stenosis. The intraoperative methylene blue infusion ensures that the blockage of the retroperitoneal perfusion from the GDA is complete.

The pump pocket will be created in the left lower abdomen so that the pump lies below the ribs to avoid contact with the iliac spine and the edge of the ribs. (Figure B) In extremely obese patients, placing the pump over the ribs should be considered, because this may help in locating and accessing the pump. The pump and catheter will be handled carefully, avoiding contact with the patient's skin. The catheter is tunneled through the abdominal wall into the abdominal cavity. The pump is secured to the abdominal fascia with nonabsorbable sutures; the catheter should be positioned behind the pump to prevent injury by a needle. The catheter that comes attached to the pump is then connected with the intra-arterial catheter that has rings close to the tip to facilitate fixating the catheter to the artery with ties.

The GDA is then ligated with a nonabsorbable tie as far away from the CHA as possible and vascular control of the common and proper hepatic arteries is achieved with vascular clamps or vessel loops. Isolated vascular control of the GDA at its orifice also can be used to avoid occlusion of the hepatic artery. An arteriotomy is made in the distal GDA, and the catheter is inserted up to, but not beyond, the junction with the hepatic artery. If the catheter protrudes into the common hepatic artery, turbulence of blood flow can lead to thrombosis of the vessel. Failure to pass the catheter to the junction leaves a short segment of the GDA exposed to full concentrations of floxuridine without the diluting effect of blood flow, potentially resulting in sclerosis, thrombosis, or late dislodgment. When positioned, the catheter should be secured with three nonabsorbable ties proximal to the tying rings on the catheter. Perfusion of both lobes of the liver and lack of extrahepatic perfusion is confirmed by a bolus injection of 2 to 3 mL of methylene blue. After the perfusion test, the catheter is flushed with heparinized saline, and the wounds are closed.

[figure not shown]

Figure B. Placement of the catheter in the gastroduodenal artery (GDA), Right gastric artery is shown adjacent to the GDA and is ligated

5.1.4.4 Postoperative procedures

Prior to the first administration of intra-arterial chemotherapy, bilobar hepatic perfusion and lack of extrahepatic perfusion are confirmed by post-operative technetium-99-labeled

macroaggregated albumin (MAA) nuclear medicine scanning. MAA is administered through the IP2000V bolus port. Within 1 hour after MAA injection, a SPECT/CT scan is performed.

In addition, a CT with contrast injection through the bolus port of the pump is performed. The contrast agent is administered through the bolus port of the IP2000V pump while acquiring images using dual source perfusion CT at a temporal resolution of 1.5 second.

Both scans are obtained after recovery from surgery, just prior to hospital discharge. Patients with extrahepatic perfusion are evaluated angiographically and aberrant branches embolized with re-testing prior to treatment. All other postoperative procedures are done according to local hospital procedures.

